PART ONE: Will answer research questions 1-4. Firstly, we will estimate the pool of potential fathers in Lothian who are on opioid substitution therapy (OST). Treating clinicians (in Lothian region) will invite eligible fathers to take part in the study, and we will enrol 24 fathers and their families in the PuP programme, thereby providing information on numbers eligible, approached and enrolled in the programme. The intervention will be delivered by twelve accredited PuP practitioners employed by four partner agencies: the City of Edinburgh Council Social Work Department 'PREPARE Team', and the Third Sector Scottish Family Support Service 'CIRCLE', Children 1st (Midlothian) and West Lothian Drug and Alcohol Service (WELDAS). PuP will be provided as an adjunct to 'treatment as usual' health and social care, including individual-based addiction treatment and child protection services. Expert PuP practitioner supervision will be provided by an accredited PuP supervisor, based in Oxford. Treatment fidelity will be monitored by asking parents to complete a bespoke PuP Treatment Experience Measure.

Qualitative interviews with enrolled fathers and mothers before starting PuP will investigate 'treatment as usual' service utilisation, including drug treatment and previous involvement with parenting and family support services. 'Usual care' for drug dependent fathers will also be explored in focus groups with referrers at the end of the implementation phase and with other key stakeholders in our 'expert event' (see below). Interviews with both parents when they complete the programme, or drop out, will explore acceptability of PuP and strategies for successful implementation. Interviews

with PuP practitioners conducted throughout the implementation phase, and focus groups with referring professionals, will explore operational issues and provide an iterative approach to feedback on programme delivery. All interviews and focus groups will be conducted by the Research Fellows and will take place in convenient locations (e.g. community 'recovery hubs' or within participants' homes).

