Progression Criteria: The following criteria will be used to guide decisions concerning the progress of the study. The research group will review these criteria on a regular basis and report to the study Steering Committee (SSC) at each of its meetings. The SSC will also be informed of any immediate concerns as these arise. The funder will be informed of the SSC's view on any matter concerning the progress of the study.

Stopping rules / Progression criteria

| Criteria | Indicator | Method of assessment |
|-------------------------|---|----------------------------|
| Successful recruitment | Trained practitioners to recruit and | Project monitoring data |
| of families to the PUP | deliver PUP to minimum of 1:5 families | |
| intervention and study. | approached or average of 2 families per | |
| | month. | |
| | Total number = 24 | |
| Delivery of PUP | PUP delivered to required standard | Bespoke treatment fidelity |
| | | measure |

| Acceptability of PUP to practitioners | Broad satisfaction of PUP among staff delivering the intervention | Qualitative interviews and regular feedback from practitioners to the research group |
|--|---|---|
| Engagement with PUP practitioners in research | 90% (7/8) of those approached agree to participate in a qualitative interview | Qualitative interview data. |
| Engagement in research with staff from agencies referring to PUP | 80% of those approached agree to participate in qualitative interview | Qualitative interview data. |
| Family engagement with PUP | 66% of families recruited complete the PUP intervention. Total = 16. | Project monitoring data |
| Acceptability of PUP to families | Broad satisfaction of PUP among families receiving the intervention | Qualitative interviews with fathers and mothers |
| Family engagement with research component to inform the development of the logic model | Minimum of 10 fathers recruited to the research study complete the baseline and end-of-treatment quantitative interviews and at least one qualitative interview | Baseline and end-of- treatment questionnaire data and qualitative interview data |
| Adverse effects | Maintain a list of all adverse effects that might arise for each family comprising those that may be attributed to the intervention and those that may be attributed to the research study. | Discussion and decision regarding the adverse effects at monthly management meetings, study steering committee and DM[E]C meetings. |

Study population

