Finally, self-regulatory skills are developed with children through combined sessions with the caregivers and child/children. These self-regulatory skills again draw from mindfulness constructs with a growing body of evidence supporting the relationship between mindfulness and adaptive emotional regulation [49] particularly for young children with difficulties with emotional regulation. These skills are appropriate for children aged 3-8 years. As parents become more emotionally regulated, they are able to provide more sensitive caregiving. This in turn, is associated with the development of emotional regulation in young children [50]. Thus, the *Parent Workbook* supports the parent by allowing for a documentation of his or her own personal journey through the programme.

Delivery of the intervention: PuP is a 20-24 week programme designed to be delivered in families' homes although, where there are concerns regarding practitioner safety, it can be delivered equally well in community-based clinical settings. For this study, PuP will be delivered by four organisations: PrePare, CIRCLE, Children 1st and WLDAS. Between them, they have 12 full-time trained practitioners (six located in CIRCLE, two in PrePare, two in Children 1st and two in WLDAS), trained by the developers of PuP ([name] and [name]), who will deliver the programme to fathers and families enrolled in this study.

CIRCLE is a Scottish National Charity for Vulnerable Children and Families which provides a community-based early years' and family support service to over 600 families per year, targeting the most disadvantaged families, especially those affected by parental substance misuse. It has purpose built facilities for working with parents, children and families but also provides a home visiting service for difficult-to-engage families. Circle is an established and highly regarded service, commissioned to provide family support services in Edinburgh, East, Mid and West Lothian by the Alcohol and Drug Partnerships, and is therefore an ideal organisation to deliver the intervention.

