Assessment of families will be conducted at baseline (prior to starting PuP), end-of-treatment (at completion of PuP or at drop-out), and at six months follow-up. In addition, parents recruited into the study during the antenatal period, who are expecting their first child, or who have no current child care responsibilities because their children are not living with them, will complete MAAS & PAAS close to the expected date of delivery (36-40 weeks gestation).

Because assessment of effectiveness is not a study aim, our feasibility assessment is described below.

Assessment of efficacy/effectiveness

Assessing training, the delivery, uptake and engagement with PuP: (Research questions 1-4 are addressed in this section). Between October 2017 and April 2018 qualitative work will be undertaken to better understand the factors that shape the implementation and uptake of PuP. This includes semi-structured interviews with PuP practitioners and recipients of the programme and focus groups with staff from referral agencies. Interviews with PuP practitioners will take place after they have completed the programme with two families. This will offer them greater opportunity to reflect on their experience. Fathers and mothers will be interviewed after they complete, or drop out of the programme. Referrers (e.g., GPs and Addiction treatment staff) will take part in a focus group at the end of the implementation phase to enable them to reflect upon the process of referral, acceptability and delivery of the programme. The interviews and focus groups will be conducted by the Research Fellows in convenient venues for staff. Recruitment data will be recorded by the Research Fellows. Attendance and completion data on each family will be recorded by the PuP practitioners using a specially designed recording sheet.

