- 1. This number is large enough to include a purposive sample of families with differing characteristics to reflect diversity within the larger population of families who would likely take part in a larger trial for example: families with concordant parents (where the mother is also drug-dependent) as well as discordant couples; younger and older fathers; first-time and experienced fathers (with more than one child), resident and non-resident fathers; biological and non-biological fathers. We will develop a sampling matrix to guide recruitment to ensure our study sample reflects the wider population of families seen in routine clinical practice. We will also document a socio-demographic profile of the sample to demonstrate the results of our sampling approach.
- 2. This sample size is also small enough to enable an in-depth analysis of the qualitative data (within the time constraints of the study) to inform our research questions around acceptability, barriers and facilitators to implementation and 'usual care' for fathers. We will conduct in-depth interviews with all parents involved in the study, as well as interviews with the PuP practitioners and focus groups with referring clinicians. We anticipate that this qualitative data will result in lengthy transcripts which will provide rich accounts of involvement in the PuP programme and study. A sample size, limited to a maximum of 24 families, will allow the research team to undertake a more detailed and critical comparative analysis of the whole data set.
- 3. This sample size also allows for an attrition rate of approx. 1/3 of families (n=8) without jeopardising the validity and rigour of the study for example, some may withdraw from the study, or drop out of the intervention or fail to complete follow-up measures. In clinical practice, many of these families stop attending services for a variety of reasons (for example, the children are taken into care, the family moves out of the catchment area, imprisonment, illness/hospitalisation etc) and attendance rates are often poor when compared to other families who have less complex needs. Thus, we calculated a desirable number of families (n=16) to complete the PuP programme and 6 month follow-up measures and then added a hypothetical but realistic attrition rate of 1/3rd to arrive at a sample size of 24 families.

Statistical analysis

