Study Steering Committee (SSC): A Study Steering Committee, nominated by the research group and appointed by NIHR will comprise an Independent Chair and other clinical and academic members and two service users. A SSC charter (approved by NIHR) will detail the role and remit of the committee, and terms of reference. The Chief Investigator ([name]) will attend SSC meetings as a non-voting member, as well as co-applicants and the RFs as required. The SSC will include the operational leads from PrePare ([name]) and CIRCLE ([name]) who will also provide routine reports on intervention implementation in the two PuP delivery sites and will liaise closely with the Chief Investigator ([name]), appointed Research Fellows and PuP practitioners within their respective services. The SSC will also include an experience statistician, [name] (University of Edinburgh), and an international expert on research involving drug dependent fathers, [name], from Yale University School of Medicine (USA). The SSG will be involved in the final decision on whether progression criteria for the development of a pilot RCT have been met.

Data Monitoring and Ethics Committee (DM[E]C): A data monitoring and ethics committee, nominated by the research group and appointed by NIHR will comprise an Independent Chair and at least two other clinical and academic members. A DM[E]C charter (approved by NIHR) will agree the role and remit of the committee, and terms of references.

Study timetable

See 'Project Management Plan 28.11.16 v1.0' which details the timetable and milestones for the study.

Key ethical considerations in this study

Risks, potential harms and benefits

Risks: Systematic reviews of parenting programmes [26-28], integrated family support programmes targeting substance-misusing parents [15, 29, 30], and previous studies of the intervention that is the subject of this study – the Parents under Pressure (PuP) programme [31] - report no adverse effects on children and families. This suggests that the risk of unintended negative consequences is minimal. However, there are potential risks which we will take into account from recruitment right through to completion.

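### The practitioner-engagement criterion equates 90% with 7/8, which is 87.5%, and its base of 8 is unexplained beside 12 practitioners

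*Protocol*

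**What the plan says.** The Stopping rules / Progression criteria table sets this indicator for engagement of PuP practitioners in the research: "90% (7/8) of those approached agree to participate in a qualitative interview". Under Outcome measures, the protocol says that the main study outcome is whether these criteria are met.

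On staffing, Part One of the Research design says: "The intervention will be delivered by twelve accredited PuP practitioners employed by four partner agencies". Delivery of the intervention itemises them as "12 full-time trained practitioners (six located in CIRCLE, two in PrePare, two in Children 1st and two in WLDAS". The Study Steering Committee paragraph, by contrast, describes the operational leads of PrePare and CIRCLE as people "who will also provide routine reports on intervention implementation in the two PuP delivery sites".

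On timing, the section on assessing training, delivery, uptake and engagement says: "Interviews with PuP practitioners will take place after they have completed the programme with two families". Part One describes interviews "with PuP practitioners conducted throughout the implementation phase, and focus groups with referring professionals, will explore operational issues".

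On completion, the progression table asks for 66% of recruited families, 16 in total, to complete PuP. Point 3 of the Sample size justification says: "This sample size also allows for an attrition rate of approx. 1/3 of families (n=8" families, again leaving 16 of 24.

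**The concern.** A progression criterion is useful only if everyone can agree afterwards whether it was met. This one states a percentage and a count as though they were the same threshold. If they differ, the result written into the criterion as the target (7 of 8) is the one on which the steering committee could not give a clear answer.

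The base raises a separate question. If all 12 practitioners are to be approached, 8 is the wrong denominator. If only eight are to be approached, the protocol does not say which eight or why.

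The timing rule matters because it may decide who is interviewed. If an interview waits until two families have completed, practitioners whose families left PuP early might not be heard, and they may be well placed to describe problems in delivery. The table's criterion of broad staff satisfaction draws partly on these interviews.

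**Working it through.** **1. The stated figure.** Inputs from the progression table: 90% and 7/8.
- 7/8 = 0.875, or 87.5%. Rounded to a whole percentage it is 88%, so the 90% is not reproduced.
- Smallest count meeting 90% of 8: 0.90 × 8 = 7.2, so 8 of 8.
- With fewer than ten approached, 90% allows no refusal. Ten is the smallest base that allows one (9/10 = 90%).

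**2. The base.** Inputs from Delivery of the intervention: 6 + 2 + 2 + 2 = 12 practitioners.
- Smallest count meeting 90% of 12: 0.90 × 12 = 10.8, so 11. Check: 11/12 = 91.7% and 10/12 = 83.3%.
- If the 7/8 proportion were kept instead: 0.875 × 12 = 10.5, again 11. With a base of 12, both versions of the threshold give the same count.
- CIRCLE plus PrePare gives 6 + 2 = 8, and the Study Steering Committee paragraph still speaks of two delivery sites. The 8 may therefore be left over from a two-agency design. This is an inference; the protocol does not say so.

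**3. The timing rule, read literally.** Inputs: 24 families, 16 planned completers, 12 practitioners, two completing families needed before an interview.
- Ceiling at 16 completers: 16/2 = 8 practitioners, so at least 12 − 8 = 4 would not qualify.
- Assumption: each practitioner has two families (24/12), and the 16 completers fall at random among the 24. The chance that both of a practitioner's families complete is (16 × 15)/(24 × 23) = 240/552 = 0.435. The expected number qualifying is 12 × 0.435 = 5.2.
- Under the same assumption the number qualifying lies between 4 and 8:

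| Practitioners with two completing families | Probability |
|---|---|
| 4 | 17.2% |
| 5 | 48.2% |
| 6 | 30.2% |
| 7 | 4.3% |
| 8 | 0.07% |

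- If families complete independently with probability 2/3, the expected number is 12 × (2/3)² = 5.3. With other completion probabilities it is 3.0 (50%), 6.8 (75%), 7.7 (80%) and 12 (100%). The figure depends heavily on completion, and 16 is a target, not a maximum.

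**The case against.** The strongest objection concerns the base. The criterion counts those approached, and the protocol never says that all 12 practitioners will be approached. A reader might infer that 8 flatly contradicts 12, but the text does not support that. It supports only that the 8 is unexplained. This objection stands.

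On timing, a reader might infer that the two-family rule shuts most practitioners out, or that no more than eight could ever qualify. Neither follows. The 16 is a completion target and more families may complete. *Most* depends on an even allocation of families that the protocol does not state. The sentence is also worded as timing, with the stated aim of giving practitioners more experience to reflect on, and nothing says that those with fewer completers are excluded. It could even mean having finished work with two families, whether or not they stayed. Because families enter at about two a month, interviews triggered this way would be spread out, so the conflict with Part One is one of wording and may be small.

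A reader might also infer that the staff-satisfaction criterion is biased upwards. The same table row also relies on regular feedback from practitioners, which carries no two-family condition, and parents who drop out are interviewed too. Bias is therefore a possibility for the interview component and has not been shown.

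Finally, this is one of nine criteria, they are described as guiding decisions, and the discrepancy turns on one person. That limits the practical effect. It does not make a threshold with two values usable.

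**Conclusion.** The percentage and the count in this criterion cannot both be the threshold. The gap is 2.5 percentage points, or one practitioner in eight, and it falls exactly on the result named in the criterion. This rests on arithmetic alone. Because the criteria form the main study outcome, it is a wrong decision threshold and not just a clerical slip, and it should be corrected before results are judged.

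The base of 8 is unexplained against a stated staff of 12. A two-agency origin is plausible but inferred.

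The timing point is secondary. The firm statement is conditional: if the rule is applied literally and 16 families complete, at least 4 of 12 practitioners would lack two completing families. The figure of about 5 qualifying needs the further assumption of two families each. Neither figure means that the engagement criterion would be failed, since practitioners who are not approached are outside its denominator.

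**What to change.** **Threshold.** State how many practitioners will be approached and give a count that matches the percentage. If all 12: at least 90% of the 12 practitioners, that is, at least 11 of 12 (91.7%). If only eight: either require 8/8, or restate the threshold as 87.5% (7/8), and in both cases give the reason for approaching eight. Check the reference to two delivery sites in the Study Steering Committee paragraph at the same time.

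**Interview timing.** Bring the two descriptions into line, and say that practitioners whose families left PuP are also interviewed, for example once their first two families have either completed or left.

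**Cost.** Wording changes to the protocol and a few more interviews by the existing Research Fellows. The drawback is that some practitioners will have less delivery experience when interviewed, which gives up part of the benefit that the two-family rule was meant to secure.

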PART TWO: Secondly, we will examine the main feasibility research questions (5-11 above) that will inform a future pilot RCT and full evaluation of PuP, in order to: test and verify methods of data collection with both parents, determine the rate at which fathers can be recruited to PuP and identify issues related to recruitment, assessment or delivery of PuP using ADePT [43] - a process which helps to systematically appraise problems and solutions encountered during a feasibility study. Our final report and recommendations will be based on the results of this process.

Qualitative interviews will ascertain acceptability of measures, including quality of caregiving based on video recording parent-child interactions and standardised measures relating to couple and family functioning, child development/wellbeing and parental substance use. Measures will be administered (by the Research Fellows) pre-treatment, end of treatment (around 24 weeks) and at six months post treatment, with completion rates examined and dose of treatment monitored. Interviews with father and mother participants will be conducted in the home where possible, or in a suitable community venue (e.g., recovery hub).

In addition, we will host an 'expert event', where key stakeholders will be invited to detail family support services for drug-dependent fathers nationwide. This data, along with qualitative data on routine service utilisation from parents enrolled in the study, will allow us to determine 'routine care pathways' for drug-dependent fathers beyond the locality of the study. This data will inform our decisions about a future study design.

Economic assessment: The feasibility of collecting suitable cost and outcome data will be investigated with a view towards a full cost-utility evaluation from a health and social service perspective as per NICE preferred reference case [44]. Parents will complete a self-report survey of NHS and criminal justice service resource use and EQ-5D-5L [45] at baseline, end-of-treatment and 6 month follow-up. NHS costs will include drug and alcohol service use, primary care consultations, secondary care consultations and community prescribing. Prescription medication will be limited to those associated with drug and alcohol treatment only in order to minimise patient burden.

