The target population for this study is 24 families, living in Lothian, with at least one child aged 0-8 years old, affected by paternal drug misuse - namely, families with fathers/male caregivers, diagnosed with opioid dependence (according to ICD-10 criteria), who are currently prescribed opioid substitution therapy (OST).

We anticipate that the majority of participants enrolled in this study will largely reflect the population of men normally enrolled in OST treatment programmes. That is, the majority will be aged between 18-55 years old, on a low income or unemployed and in receipt of welfare benefits, living in social housing in areas of deprivation, and have a history of poly-drug use and criminal justice involvement, including imprisonment. Many of the parents will have complex needs e.g. poor physical health/blood borne viruses, mental health issues (anxiety and depression), a history of trauma and/or childhood abuse and neglect themselves. Typically, these parents present with emotional dysregulation, poor problem solving and coping skills, low educational attainment, limited social skills, and problems with debts/budgeting, housing stability and employability.

Our recruitment strategy will aim to include a diverse range of fathers and families who broadly reflect the diversity of family constellations which are now common place amongst this population. Thus we will include:

- biological and non-biological ('social' or 'step') fathers
- resident and non-resident fathers, so long as the father plays an active role in the day-to-day care of the children
- concordant couples (where both the father and the mother are drug-dependent)
- discordant couples (where only one adult in the family the father is drug-dependent).

By adopting a 'real life' approach to fathering and fatherhood diversity, we aim to enhance the clinical relevance and ecological validity of the study findings. We propose to take a pragmatic approach and include any male partner who is a caregiver to one or more children and defines himself as a 'father', 'father figure' or 'male caregiver' to a preschool aged child. This is in keeping with Panter-Brick et al's [3] systematic review which defined the term 'father' as "all men who are socially significant to children or assume actual fatherly roles in taking care of children, whether or not the birth father, married to the mother, or co-resident with the child" pg1191.

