Recruitment: Participants will be recruited into this study (approximately two families per month) via the following services: NHS Lothian Substance Misuse Directorate/Integrated health and social care teams in Lothian, Primary Care Teams in Lothian, CIRCLE, PrePare, Children 1st and WLDAS. A study invitation letter will be prepared and sent out to all recruitment sites. This will include information on the study, participant eligibility criteria, participant information sheets, and clear instructions on how to refer into the study. Meetings with staff teams will be offered to answer any questions about the study and the intervention. Staff will be asked to identify eligible fathers (prescribed opioid substitution therapy) and their families when they attend for routine appointments and, if they show an interest in the study, with their permissions, pass their contact details onto the research team. Treating clinicians will be advised to log in the patient's notes that they have agreed to be contacted. The research team will contact (via study mobile phone) potential participants (fathers and mothers separately) to discuss the study and PuP programme in more detail and will obtain informed written consent if they both wish to take part.

The consent process will involve: agreement regarding confidentiality (including the limits of confidentiality in respect of child and adult protection and legal issues), permissions regarding data collection (including audio and video recording and follow-up), data protection and data management, anonymity, GP notification, payment of all expenses, and freedom to withdraw from the study. Children in the family, who are deemed to have the capacity to consent, who wish to participate in the intervention will also be consented into the study, after their parents agree to the child being approached by the research team. Likewise, kinship carers or other family members who wish to take part in the programme will be asked to provide consent to take part, after agreement

with the parents and allocated PuP practitioner. Please note: If any young person or significant other does not wish to take part in the study, the PuP programme will be delivered with only those whom consent has been obtained.

Drop-outs: Additional measures will be taken to ensure retention of fathers and to maximise follow-up of drop-outs. When we enrol participants we will seek permission to:

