Assessing recruitment, gathering research data, assessing impact, and a future study: (Research questions 5 – 11 are addressed in this section). Routine data collected by the Research Fellows between May 2017 and October 2018 will provide: detailed quantitative data on participant flow through the study comprising recruitment rates, numbers providing informed consent and numbers completing the outcome measures at baseline, end-or-intervention and at six months follow up. Researcher field notes will provide the reasons for these rates and the best methods of recruiting and retaining participants in the study. We anticipate that we will need to be flexible and dynamic to maximise retention of families, particularly at six months follow-up. All difficulties and solutions (e.g. change of address/mobile phone numbers, use of text messaging and reminders), will be recorded in the final report. At each research interview we will ask families to provide their views on the acceptability and appropriateness of all the measures, including the economic measures, for example, time taken to complete and level of intrusiveness. In addition, we will explore the parent's willingness to provide consent in the future for their routinely collected data to be used in future studies that link data sets to answer questions about long term outcomes.

Although our predominant focus is on questions of feasibility, we will provide an indication of the possible impact of PuP. Analysis of change will include a calculation of the clinical significance of change using the *reliable change index [51]*. The focus will be on measures of parental emotion regulation; emotional availability/antenatal attachment and child abuse potential. Data will be synthesised in the final report and recommendations made as to whether a pilot trial should be conducted and if so, what features should be considered including an economic evaluation. We will use the ADePT process to guide our recommendations [43].

Sample size justification

Our main justification for the sample size of 24 families with a father/male caregiver who is on opioid substitution therapy (OST) is related to the qualitative data collection and analysis requirements, namely:

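### At the stated two families a month, only about 13 to 15 of the 24 families would fall due for 6-month follow-up before data collection closes in October 2018, against 16 planned to complete it

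*Protocol*

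**What the plan says.** - **Rate and target.** Procedure/Methods, Recruitment: "Participants will be recruited into this study (approximately two families per month) via the following services". Study population: "The target population for this study is 24 families, living in Lothian". The progression criteria table gives the same monthly average as one of two alternative recruitment indicators.
- **Time to follow-up.** Delivery of the intervention gives PuP a length of 20 to 24 weeks. Research design, Part Two, places the later assessments at "end of treatment (around 24 weeks) and at six months post treatment". Quantitative data analysis also counts the six months from the end of treatment.
- **Data window.** Assessing recruitment, gathering research data, assessing impact, and a future study: "Routine data collected by the Research Fellows between May 2017 and October 2018 will provide" recruitment, consent and completion figures for baseline, end of intervention and six months.
- **Follow-up target.** Sample size justification, point 3: "we calculated a desirable number of families (n=16) to complete the PuP programme and 6 month follow-up measures". One-third attrition is then added to reach 24.
- **Interview window.** Assessing training, the delivery, uptake and engagement with PuP: "Between October 2017 and April 2018 qualitative work will be undertaken". Parents are interviewed there after completing or leaving the programme. Sample size justification, point 2, expects in-depth interviews with every parent in the study.

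**The concern.** Each family needs 20 to 24 weeks of PuP plus six months before its last assessment, which is nearly a year. Enrolment at the stated rate also takes a year. The data window is 18 months, so the later families cannot reach follow-up inside it.

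Two things are at stake. First, point 3 of the sample size justification relies on a number of 6-month completers that the stated dates do not yield. Second, objective 6 is to determine retention for a future trial, and follow-up is to be summarised as counts and percentages. If families whose visit had not yet fallen due were counted as not followed up, the end of data collection would look like drop-out and the retention estimate would be too low.

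**Working it through.** **The plan's own figure.** 16 / (1 − 1/3) = 24, and 24 × 2/3 = 16. The inflation is correct, but 16 completers at that attrition require all 24 families to fall due for follow-up.

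**Inputs.** Two families a month; 24 families; PuP of 20 or 24 weeks; follow-up six months after treatment; window from 1 May 2017 to 31 October 2018, with both end months counted in full; attrition of 1/3. The first enrolment is assumed to be on 1 May 2017. That agrees with the interview window: 1 May 2017 plus 24 weeks is 16 October 2017, the month in which that window opens.

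**Last family.** 24 / 2 = 12 months, so enrolment runs to about 30 April 2018.
- 24 weeks: end of treatment 15 October 2018, follow-up 15 April 2019.
- 20 weeks: end of treatment 17 September 2018, follow-up 17 March 2019.

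All 24 families can therefore end treatment inside the window, but the last follow-up falls about 4.5 to 5.5 months after it closes.

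**Families due by 31 October 2018.** Latest enrolment = 31 October 2018 − 6 months − programme length. Families due = 2 × months from 1 May 2017 to that date.

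| PuP length | Latest enrolment | Months | Families due | × 2/3 |
|---|---|---|---|---|
| 24 weeks | 13 Nov 2017 | 6.44 | 12.9 | 8.6 |
| 20 weeks | 11 Dec 2017 | 7.36 | 14.7 | 9.8 |

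**Sensitivity.**
- Varying the day of enrolment within the month gives 12 to 14 due (24 weeks) or 14 to 16 due (20 weeks).
- The most favourable case is a uniform 20-week programme with both families enrolled on the first of each month: 16 due before any loss, and 16 × 2/3 = 10.7 after it.
- If the window closes on 1 October 2018, 11.0 (24 weeks) or 12.8 (20 weeks) are due.
- For all 24 to be due by 31 October 2018, the rate must be 24 / 6.44 = 3.7 a month (24 weeks) or 24 / 7.36 = 3.3 a month (20 weeks).

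**Effect on a rate taken over all 24.** With perfect retention it would read about 13/24 = 54% (24 weeks) or 15/24 = 62.5% (20 weeks).

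**Interview window.** It closes in April 2018. 30 April 2018 less 24 weeks is 13 November 2017; less 20 weeks it is 11 December 2017. Families enrolled later who complete PuP finish after the window. At the stated rate that is about 24 − 15 = 9 to 24 − 13 = 11 families, before drop-out.

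**The case against.** The strongest reply is that the rate is approximate, that the progression table treats it as an average attached to a minimum, that no recruitment start date is given, and that the detailed timetable sits in a separate project management plan that is not shown. This stands so far as to make the conclusion conditional. A reader might infer that 16 is unattainable in any event, or that 13 is a ceiling. The documents support neither: faster recruitment would narrow the gap, and 13 belongs to the 24-week case. But the only rate stated is about two a month, and if the separate timetable runs follow-up past October 2018, the closing date in the Protocol is wrong.

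A reader might also infer that the whole sample size, or progression to a trial, collapses. It does not. The Protocol gives qualitative requirements as the main reason for 24, and the 16 with 6-month data appears only in the third point, as something desirable. The progression table asks for 16 families completing PuP and at least 10 fathers with baseline and end-of-treatment data and one qualitative interview. No criterion uses 6-month data, and all remain reachable.

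Nor does any section say that the follow-up rate will be taken over all 24. The CONSORT-style flow summary and the field notes give room to separate families not yet due from those lost. The denominator problem is therefore a risk to close off and not an error already made.

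On interviews, Part One also plans them before PuP starts, and parents who leave early are interviewed when they leave. Only post-programme interviews with later completers are in conflict.

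**Conclusion.** The concern holds as a conditional inconsistency. At about two families a month from May 2017, about 13 to 15 of 24 families fall due for 6-month follow-up by the end of October 2018, and about 9 to 10 complete it at the plan's own attrition, against 16. No variant examined at the stated rate gives more than about 11 after attrition. The result rests on the inferred start date and a steady rate. The damage is confined to the third sample-size argument, the 6-month outcome and retention estimates, and post-programme interviews with families enrolled after about mid-November to mid-December 2017.

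**What to change.** 1. Reconcile the recruitment rate, the two data windows and point 3 of the sample size justification against actual enrolment dates. The version shown is v4.0 of 11 June 2018, after the nominal end of recruitment, so those dates should be known.
2. Either restate the number expected with 6-month data (at the nominal rate, about 13 to 15 due and about 9 to 10 completing), or correct the closing date. At the nominal rate the last follow-up is in mid-March to mid-April 2019.
3. Report the 6-month follow-up rate over families whose visit fell due before data close, and show families not yet due separately from drop-outs in the flow summary.
4. Align the post-programme interview window with the last end of treatment, about October 2018 at the nominal rate.

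Items 1 and 3, and the restatement in item 2, cost only wording and a less favourable stated number. Item 4 lengthens the interview period but stays inside the data window already stated. If the closing date were moved because fieldwork really is to run longer, more time and probably the funder's agreement would be needed, and the result would have to fit the 24 months set under Research objectives.
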